6.1.3.1 Model checking procedures

Missing data will be assumed to be missing at random and thus the above analysis will be performed on all available data. There will be no imputation of missing data.

The interaction between treatment and day will be assessed, and if non-significant, the results from the 3 days will be averaged and corresponding model-based quantities extracted.

The model assumption of negative binomial distribution will be examined, especially if over-dispersion (i.e. variance>mean) exist. If the data doesn't fit negative binomial distribution or over-dispersion doesn't exist, other models such as Poisson regression will be explored.

The model assumption of no first-order carry-over effect may be evaluated by incorporating first-order carry-over effects into the above statistical models, and performing a type 3 test for the first order carry-over effect. In addition, descriptive summary statistics will also be provided by treatment sequence and visit in order to assess carry-over effect.

6.1.3.2 Graphical presentation of results

Least-square mean and least-square mean difference between treatments with 80% confidence intervals will be plotted by treatment for daily number of stools with a BSC score of 6 or 7 and daily number of bowel movements.

6.2 Secondary objectives

6.2.1 Variables

- Three-day total number of stools with a BSC score of 6 or 7 per period
- Three-day total number of bowel movements per period

Over each 24 hour collection period:

- Average stool consistency with Bristol stool chart

It is defined as arithmetic average of consistency for all stools collected during 24 hour period.

- Average stool pH

It is defined as arithmetic average of PHs for all stools collected during 24 hour period.

- Average stool weight

It is defined as arithmetic average of weights for all stools collected during 24 hour period.

6.2.2 Descriptive analyses

All secondary endpoints will be listed by treatment sequence, subject, and visit/sampling time point. Descriptive summary statistics will be provided for the observed values and change from baseline by treatment and visit/period. Summary statistics for the three-day total number of episodes of diarrhea, average stool consistency, pH, and weight will include mean (arithmetic), SD, median, minimum and maximum. Observed Mean (SD) plot will be produced for all secondary endpoints.

6.2.3 Statistical model, assumptions and hypotheses

[figure not shown]
Three-day total number of stools with a BSC score of 6 or 7 per period will be analyzed by a negative binomial mixed effects model with random effect of subject and fixed effects of period and treatment. Change from baseline in three-day total number of bowel movements per period will be analyzed by a linear mixed effects model with random effect of subject and fixed effects of period, treatment and baseline three-day total number of bowel movements. Secondary endpoints including average stool consistency, PH and weight will be analyzed by a linear mixed effects model with random effect of subject and fixed effects of period, treatment, and baseline measurement. The least-squares mean and associated 80% CI for each treatment, and the estimated mean difference between each treatment, the p-value, and corresponding two-sided 80% CI, will be extracted from the model, and summarized.

[figure not shown]

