7.2 Discontinuation of study treatment

Discontinuation of study treatment for a subject occurs when study treatment is stopped earlier than the protocol planned duration. Discontinuation of study treatment can be decided by either the subject or the investigator.

Study treatment must be discontinued under the following circumstances:

[figure not shown]
- Subject decision - subjects may choose to discontinue study treatment for any reason at any time.
- The investigator believes that continuation would negatively impact the safety of the subject or the risk/benefit ratio of trial participation.
- Any protocol deviation that results in a significant risk to the subject's safety.
- Pregnancy
- Use of prohibited treatments.

Study treatment of individual subject will be discontinued when that subject experiences:

- Clinically significant diarrhea, suspected to be related to the study drug, that may put the subject at risk at the discretion of the investigator and in consultation with the sponsor
- Clinically significant symptomatic orthostasis confirmed by repeated orthostatic blood pressure changes (more than a 20 mmHg drop in systolic or 10 mmHg drop in diastolic blood pressure and increase in heart rate >20 bpm (compared to the sitting results) when blood pressure and pulse are taken after at least 3 minutes standing)
- Clinically significant urinary tract or genitourinary infections, at the discretion of the investigator and in consultation with the sponsor if deemed necessary.
- Clinically symptomatic hypoglycemia confirmed by repeated blood glucose levels (<56 mg/dL).
- Ketoacidosis (symptoms of ketoacidosis include nausea, vomiting, abdominal pain, unusual tiredness and trouble breathing) confirmed by blood pH and ketones bodies in both plasma and urine.
- Any laboratory abnormalities that in the judgment of the investigator, taking into consideration the subject's overall status, prevents the subject from continuing participation in the study.
- Any hospitalization, or other SAE, that is suspected to be related to the study treatment.

If discontinuation of study treatment occurs, the investigator must determine the primary reason for the subject's premature discontinuation of study treatment and record this information on the Dosage Administration CRF.

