11.5 Analysis of secondary variable(s)

11.5.1 Efficacy / Pharmacodynamics

The three-day total number of episodes of diarrhea per period will be summarized by treatment, and analyzed using a negative binomial model with fixed effects of subject, period and diet. The least-squares mean and associated 80% CI for the three-day total number of diarrhea episodes per period for each treatment, and the estimated mean difference between each treatment, the p-value, and corresponding two-sided 80% CI, will be extracted from the model, and summarized by a table and a line chart.

The model assumption of no first-order carry-over effect and the negative-binomial distribution may be evaluated in a similar fashion as the primary endpoint.

Other secondary endpoints include average consistency with Bristol stool chart, average stool pH, average stool weight over each 24 hour collection period. They will be summarized by treatment, and analyzed by a linear mixed model with fixed effects of subject, period, treatment, and baseline measurement. The least-squares mean and associated 80% CI for each treatment, and the estimated mean difference between each treatment, the p-value, and corresponding two-sided 80% CI, will be extracted from the model, and summarized by a table and a line chart.

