6.2.3.1 Model checking procedures

[figure not shown]
The model assumption of no first-order carry-over effect and negative binomial distribution will be examined for three-day total number of stools with a BSC score of 6 or 7 per period and three-day total number of bowel movements per period similarly to the primary endpoint. Missing data will be assumed to be missing at random and thus the above analyses will be performed on all available data. There will be no imputation of missing data.

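### The model for the three-day total of BSC 6/7 stools does not allow for days observed, so the treatment ratio may be pulled toward 1 if diarrhea cuts short more reference periods than others.

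*SAP*

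**What the plan says.** SAP 6.2.1 names the endpoint, "Three-day total number of stools with a BSC score of 6 or 7 per period", but gives no rule for forming the total when a day is missing. The same section does define how average consistency, pH and weight are formed.

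SAP 6.2.3 gives the analysis: "Three-day total number of stools with a BSC score of 6 or 7 per period will be analyzed by a negative binomial mixed effects model". Subject enters as random; period and treatment are fixed. Protocol 11.5.1 has the total "analyzed using a negative binomial model with fixed effects of subject, period and diet". Neither contains an offset, an exposure term or a minimum number of days.

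On missing data, SAP 6.2.3.1 says "Missing data will be assumed to be missing at random and thus the above analyses will be performed on all available data" and "There will be no imputation of missing data".

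Protocol 7.2 lists "Clinically significant diarrhea, suspected to be related to the study drug" among the reasons for ending an individual's treatment, at the investigator's discretion and in consultation with the sponsor. Protocol 6.5 permits no interruptions and has treatment discontinued for subjects who cannot tolerate it. Protocol 7.2 adds that a subject who stops treatment remains in the study unless consent is withdrawn.

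**The concern.** A sum over one or two days is not comparable with a sum over three. If it enters the model as it stands, each unobserved day counts as zero loose stools. That amounts to an imputation, and assuming missing at random does not repair it.

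The shortfall is unlikely to be balanced if the study's own premise is right. SAP 6.1.3 expects more loose stools with 50% carbohydrate and with no supplement, and diarrhea is a reason to stop. Short periods would then fall mostly in the reference arm, lower its mean total and make the diet or supplement look less effective. The primary daily model simply leaves an unobserved day out, so the two analyses could disagree on the same data.

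**Working it through.** **Planning figures (Protocol 11.7).** Five completers per sequence and 37.5% drop-out give 5/(1 − 0.375) = 8 per sequence, and 30/(1 − 0.375) = 48 in all. Both match the plan. Simulated power with 15 completers per part was 86.5-89.7% at two-sided 0.20, the level that matches the 80% intervals. The plan does not state its alpha. These figures are not in dispute. They supply the two effect sizes used below: 3 to 1.5 episodes per day (ratio 0.50, totals 9 and 4.5) and 5 to 3 per day (ratio 0.60, totals 15 and 9).

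**Closed form.** Let a share q of reference periods be cut after day d, with no comparator period cut and partial sums entered:

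expected reference total = 3·m0·[1 − q·(3 − d)/3]; apparent ratio = 3·m1 / expected reference total.

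Example: m0 = 3, m1 = 1.5, q = 0.10, d = 1 gives 9 × (1 − 0.0667) = 8.4, and 4.5/8.4 = 0.536.

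| Reference periods cut (assumed) | True 0.50, after day 1 | True 0.50, after day 2 | True 0.60, after day 1 | True 0.60, after day 2 |
|---|---|---|---|---|
| 5% | 0.517 | 0.508 | 0.621 | 0.610 |
| 10% | 0.536 | 0.517 | 0.643 | 0.621 |
| 20% | 0.577 | 0.536 | 0.692 | 0.643 |
| 37.5% | 0.667 | 0.571 | 0.800 | 0.686 |

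If the same share is cut in both arms, the factor cancels. The ratio stays at 0.50 or 0.60 and only the least-squares means fall.

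**Simulation.** The closed form ignores the fact that periods ended by diarrhea have high daily counts. A simulation therefore let a high daily count end that period and all later ones: 120 trials of 24 subjects per scenario, Poisson daily counts, a gamma subject effect with variance 1 or 2.4 (the plan's dispersion values), and a negative binomial model with a normal random subject effect. The stopping triggers, and hence the shares cut, are assumptions. Median ratios:

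| Means per day, dispersion | Cut: reference / other | Partial sums | Incomplete dropped | With log(days) offset | Full data |
|---|---|---|---|---|---|
| 3 vs 1.5, 1 | 7% / 1% | 0.525 | 0.514 | 0.500 | 0.500 |
| 3 vs 1.5, 1 | 20% / 4% | 0.550 | 0.528 | 0.482 | 0.481 |
| 3 vs 1.5, 2.4 | 6% / 1% | 0.506 | 0.491 | 0.477 | 0.477 |
| 5 vs 3, 1 | 11% / 3% | 0.629 | 0.612 | 0.588 | 0.586 |

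The comparison is within rows. With partial sums the shift from full data is 0.025, 0.069, 0.029 and 0.043. With incomplete periods dropped it is 0.014, 0.047, 0.014 and 0.026, which is 56%, 68%, 48% and 60% as large. The offset returns the estimate to within 0.002 of full data.

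The offset does less well when counts also vary from day to day within a subject. In a separate simulation with within-subject dispersion of 0.3-0.4 (assumed) and a fixed-subject Poisson model, it removed roughly 60-100% of the bias. A true 0.50 gave 0.53-0.56 from partial sums and 0.51-0.52 with the offset.

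**The case against.** **Partial entry is not written down.** A reader might infer that the plan treats a one-day or two-day period as a full total. It does not say so. Setting an incomplete total to missing fits the no-imputation sentence at least as well. This stands, but that reading also moves the ratio toward 1, about half as far or somewhat more, so a rule is needed either way.

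**Stopping drug is not stopping observation.** Subjects are domiciled, stools are collected through washout, and those who stop treatment are not withdrawn unless they withdraw consent. A shortened treatment period may therefore still have three days of stool data, partly off drug. This stands, and it shapes the fix: an offset for all observed days would change nothing in such a period. Stool count and offset must cover the same dosed days.

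**The 37.5% is not a within-period rate.** It might be read as the share of periods at risk. It is whole-study drop-out used to inflate the sample size, and Protocol section 4 expects at least 36 of 48 to complete, a loss of 1 − 36/48 = 25%. A subject who leaves between periods creates no partial total. Protocol 1.3.1 reports no LIK066-related withdrawals from treatment for adverse events. The planning counts also come from 50 mg three times daily, whereas this study gives 50 mg once daily. All of this argues for small shares.

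**The endpoint carries little weight.** Protocol 11.8 plans no formal testing of secondary variables, and the study is non-confirmatory. A reader might connect this total with the plan's conclusion from all three days together, but that sentence belongs to the primary daily model. This limits the importance. Least-squares means, p-values and 80% intervals for the total will nonetheless be reported and plotted.

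**Conclusion.** The gap holds: neither document allows for days observed or covers an incomplete period. The bias is conditional. It needs diarrhea-related stopping to shorten more reference periods than others, and either partial sums to enter or incomplete periods to be dropped. Under those conditions the ratio moves toward 1 by a few hundredths at 5-10% of reference periods cut. The 37.5% row is an extreme case with no support in the documents as a within-period rate.

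Two stronger readings are not supported. The documents do not show that the effect will be biased, because equal cutting leaves the ratio alone and the shares cut are unknown. The primary result is also not compromised. This is a minor point, worth correcting because the correction is standard and cheap.

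**What to change.** In SAP 6.2.1, define the total as BSC 6/7 stools over dosed days with stool data, and say how periods with fewer than three such days are handled. In SAP 6.2.3, add an offset of log(number of those days) to the negative binomial model. Alternatively, derive the three-day mean from the primary daily model whatever the result of the treatment-by-day test. SAP 6.1.3.1 currently averages the days only if that interaction is non-significant.

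State a matching rule for the three-day bowel-movement total, where a short period would otherwise be compared with a three-day baseline. One option is the mean per dosed day observed, with baseline on the same scale. Report the number of days observed by treatment.

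The cost is one model term, a few SAP sentences and one small table, with no new data. The drawback is that the estimate becomes an on-treatment daily rate that assumes unobserved days resemble observed ones. The SAP should say so.

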3.1 Study design

This study employs a randomized, open-label, two-part, three-period, cross-over design. This is a non-confirmatory study. Each part of the study will enroll approximately 24 overweight or obese subjects, thus, a total of approximately 48 subjects will be enrolled for the entire study. In each part of the study, each subject will be randomized to one of the 3 treatment sequences shown in [Figure 3-1](#) (Part A) and [Figure 3-2](#) (Part B).

Part A of the study will assess the effects of % carbohydrate (50%, 25% and 0%) in the breakfast meals on diarrhea when LIK066 is administered immediately before the breakfast. Part B of the study will assess the effects of a concomitant treatment with a supplement (calcium carbonate or psyllium) on diarrhea when LIK066 is administered immediately before a breakfast meal with 50% carbohydrate.

The primary endpoint of this study is the diarrhea events. Diarrhea is usually defined by reduced consistency and/or increased frequency of stools. Normal stool frequency ranges from 3 per week to 2 per day. Bristol Stool Chart (BSC) is frequently used as a measure of consistency, and a score of 6 or 7 (pourable or watery stool) is considered abnormal. Diarrhea events will be captured based on both reduced consistency (stools with BSC score of 6 or 7) and increased frequency (total number of bowel movements, total number of stools with BSC of 6 or 7). Symptoms such as urgency, bloating, flatus, and abdominal pain will also be recorded for each bowel movement.

The study will consist of an up to 24 day screening period, a 3 day baseline/run in period, and three periods of treatment of 3 days each with a 5 day washout period in between each treatment period. Study completion will occur 3 days after the last dose of LIK066. The baseline, treatment and washout periods will be conducted with subjects being domiciled for approximately 25 days (see [Figure 3-1](#) and [Figure 3-2](#)).

Screening (Day-28 to Day -4)

[figure not shown]
Potential study subjects will present to the clinical site for a screening visit where eligibility for the study will be evaluated.

Baseline/Run In (Day-3 to Day -1)

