Subjects who meet the inclusion/exclusion criteria at screening will be admitted to the clinical site on Day -3. A survey for food preference of each subject will be conducted so that meal menus can be provided to accommodate the usual diet habits of each individual. As diet changes may impact on the bowel movement habits, subjects participating in this study will be encouraged to follow their usual dietary habit whenever possible.

During the baseline period, a standardized breakfast meal (600 calories with 50% carbohydrate, 15% protein and 35% fat) will be served; for lunch and dinner, menu options will be offered so that each subject can follow their usual diet following the standard nutritional guidance.

Starting on Day-3 and continuing through the 25 days of domiciling period, stool assessments will take place whenever a subject has a bowel movement ([Assessment schedule](#)). Starting from Day -2 at approximately 07.00, a 24-hour stool collection will be done for each subject. During Day -2 through Day 22, daily bowel movements will be monitored and collected, and stored in a refrigerated container and will be assessed by the study staff according to the Bristol Stool Chart and bowel movement record.

The stool assessments include recording of the timing, weight, pH, consistency of stool using Bristol Stool Chart, [REDACTED]

[REDACTED] according to the

[Assessment schedule](#).

Day -1 Baseline Assessment

Twenty-four (24) hour baseline stool samples will be collected from Day-1 to Day 1 morning (approximately 07.00 to 07.00) for various assessments of fecal parameters according to the [Assessment schedule](#).

[REDACTED]

On Day -1, at approximately 07.30, a 600 calorie standardized breakfast meal containing 50% carbohydrate, 15% protein, and 35% fat will be served, and subjects will drink 250 mL water immediately before breakfast during treatment periods. The time of drinking water will be defined as time zero for the measurement of baseline PD endpoints. Each subject will consume the designated breakfast within 15 mins. [REDACTED]

[REDACTED] Lunch will be served at approximately 13.00 (after completion of the PD sample collection and at least 5 hours from breakfast), and dinner will be served at approximately 18.30. The timing of meals should be harmonized on all days (Day -1, Day 3, Day 11, and Day 19) when PD are measured to minimize the effects of diurnal rhythm.

[REDACTED]

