6.1.3 Statistical model, assumptions and hypotheses

The primary efficacy hypotheses are that the mean daily number of stools with a BSC score of 6 or 7 /change from baseline in daily number of bowel movements in:

1. the 50% carb group is higher than other groups with lower carbs
2. the no supplement group is higher than other groups with supplement.

The primary analysis will be performed by study part. The daily number of stools with a BSC score of 6 or 7 will be analyzed using a negative binomial mixed effects model with fixed effects of period, treatment, day, the period-by-day interaction, and the treatment-by-day interaction, and a random subject effect. An unstructured covariance matrix will be specified for the repeated observations on a subject within the same period. The least-squares mean and associated 80% CI for the daily number of stools with a BSC score of 6 or 7 for each treatment, and the estimated mean difference between each treatment, the p-value, and corresponding two-sided 80% CI, will be extracted from the model for each day, and summarized. Mean difference will then be exponentiated as ratio between treatments means. Conclusions from the analysis will be based on treatment differences from all 3 days, collectively.

Change from baseline in daily number of bowel movements will be analyzed by a linear mixed effects model with fixed effects of baseline daily number of bowel movements, period, treatment, day, the period-by-day interaction, and the treatment-by-day interaction, and a random subject effect. An unstructured covariance matrix will be specified for the repeated observations on a subject within the same period. Baseline is defined by the last daily measurement before dosing. If day -1 measurement is missing, day -2 or day -3 measurements will be used instead. The least-squares mean and associated 80% CI for each treatment, and the estimated mean difference between each treatment, the p-value, and corresponding two-sided 80% CI, will be extracted from the model and summarized.

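### Average stool consistency, pH and weight are adjusted for a baseline value that does not exist without a baseline stool, and the SAP does not say which run-in days supply it

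*SAP*

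**What the plan says.** SAP 6.2.3 specifies for the three stool averages a "linear mixed effects model with random effect of subject and fixed effects of period, treatment, and baseline measurement". Protocol 11.5.1 also adjusts for baseline but fits subject as fixed: a "linear mixed model with fixed effects of subject, period, treatment, and baseline measurement".

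SAP 6.2.1 defines the variables per 24-hour collection. For pH: "It is defined as arithmetic average of PHs for all stools collected during 24 hour period". Consistency and weight are defined in the same way, so weight is an average per stool and not a 24-hour total. SAP 6.2.3.1 adds: "There will be no imputation of missing data".

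SAP 6.2 gives no definition of baseline. The only one in the SAP is in 6.1.3, in the paragraph on the bowel-movement count: "Baseline is defined by the last daily measurement before dosing", followed by "If day -1 measurement is missing, day -2 or day -3 measurements will be used instead". Protocol 3.1 describes the baseline collection for fecal parameters as a single day: "Twenty-four (24) hour baseline stool samples will be collected from Day-1 to Day 1 morning". It also starts 24-hour collection on Day -2 and per-stool assessment on Day -3. In the footnotes to Table 8-1, pH belongs to the 24-hour collection, while mass and consistency are recorded at each bowel movement.

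On how often a stool may be expected, protocol 3.1 states: "Normal stool frequency ranges from 3 per week to 2 per day".

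**The concern.** A 24-hour interval without a stool is ordinary at the lower end of the protocol's normal range. For a count, that day is a valid zero. For an average over stools it is zero divided by zero, and no value exists. A mixed model cannot use a record whose covariate is missing, so one stool-free baseline collection can remove all of a subject's treatment-period records from all three models.

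Two things are at stake. The first is precision, in parts of only 24 subjects. The second is representation, because the subjects removed are those with infrequent stools. In return the model gets a covariate with one value per subject, which can do little for a cross-over contrast estimated within subjects. Because the baseline rule is unstated, two competent programmers could also analyse different sets of subjects.

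**Working it through.** **Plan's own figure.** Protocol 11.7 needs 5 completers per sequence and assumes 37.5% drop-out: 5/(1 - 0.375) = 8 per sequence, 30/(1 - 0.375) = 48 in total. This reproduces, and gives 24 per part, of whom 24 × 0.375 = 9 are expected to drop out. That calculation concerns the primary stool count. Protocol 11.8 gives no power for the secondary variables.

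**1. Loss of subjects.** Inputs are the stool rates from protocol 3.1 (3 per week = 3/7 = 0.43 per day, and 2 per day), with 1 per day as an intermediate value. Let λ be the daily rate and k the number of run-in days that may supply the baseline. The documents give no distribution, so two are used:

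- Poisson: P(no stool) = exp(-λk)
- Evenly spaced: P(no stool) = max(0, 1 - λk)

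The SE multiplier is 1/√(1 - P), assuming losses are balanced over sequences.

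| Rate | Days counted | Poisson P | Lost of 24 | SE multiplier | Evenly spaced: lost of 24 |
|---|---|---|---|---|---|
| 3/week | -1 | exp(-3/7) = 65% | 15.6 | 1.694 | 13.7 |
| 3/week | -2, -1 | exp(-6/7) = 42% | 10.2 | 1.318 | 3.4 |
| 3/week | -3 to -1 | exp(-9/7) = 28% | 6.6 | 1.176 | 0 |
| 1/day | -1 | exp(-1) = 37% | 8.8 | 1.258 | 0 |
| 1/day | -2, -1 | exp(-2) = 14% | 3.2 | 1.075 | 0 |
| 1/day | -3 to -1 | exp(-3) = 5% | 1.2 | 1.026 | 0 |
| 2/day | -1 | exp(-2) = 14% | 3.2 | 1.075 | 0 |
| 2/day | -2, -1 | exp(-4) = 2% | 0.4 | 1.009 | 0 |
| 2/day | -3 to -1 | exp(-6) = 0.2% | 0.1 | 1.001 | 0 |

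The two-day rows may be the most that pH can offer, since its 24-hour collection starts on Day -2.

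**2. What the covariate gains.** Generalised least-squares variances were computed for the three-sequence Latin square with 24 subjects, with and without a subject-level baseline. Assumed: intraclass correlation 0.3, 0.5 or 0.7, and correlation of baseline with the subject effect 0.3, 0.5 or 0.8.

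- Complete data: the SE ratio with/without baseline is 1.000 in every setting. In one simulated data set fitted by REML, the two treatment estimates (-0.37873 and -0.67252) and their SE (0.21622) are identical with and without it.
- Nine of 24 dropping out after period 1 or 2: the mean SE ratio runs from 0.9999 to 0.9859, a gain of 0.01% to 1.4%. The best single replicate is 0.9725, a gain of 2.8%.
- Protocol version with fixed subject effects: 24 subject columns + 2 treatment + 2 period = 28. Adding baseline makes 29 columns, but the rank stays at 28, so the covariate is fully aliased.
- Per-treatment means: in the simulated data set the intercept SE falls from 0.286 to 0.249 with baseline, so the LS means do gain.

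**3. Trade-off for the treatment difference.** Losing one subject of 24 multiplies the SE by √(24/23) = 1.022, a cost of about 2.2%. That exceeds the largest average gain (1.4%) and is close to the best single replicate (2.8%). Losing two costs √(24/22) = 1.044, more than any gain seen.

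**The case against.** A reader might infer that every subject without a Day -1 stool is certain to be deleted. The documents do not establish this. The SAP's one baseline rule does fall back to earlier run-in days, and SAP 6.2 is silent, which is not the same as excluding the fallback. That point stands. Equally, nothing extends the rule to the stool averages. It was written for a count, where a stool-free day is a zero and not a missing value, and the protocol labels a single day as the baseline fecal collection.

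A reader might also take 16 of 24 as the expected loss. That figure needs Poisson counts and every subject at the lower limit of normal. The protocol's range extends to 2 per day, and with regular stools at 1 per day or more nothing is lost. It is one end of a range.

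It is also tempting to say that the covariate adds nothing and can be dropped without cost. That is exact only for the treatment difference with complete data. The SAP uses a random subject effect, drop-out is planned for, and LS means with 80% CIs are reported and plotted, so there is a small gain under drop-out and a visible one for the LS means.

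Finally, coding weight as 0 on a stool-free day might look like a remedy. It does not fit the endpoint as defined: an average per stool is undefined there, and a zero would silently turn it into something else.

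The limited role of these endpoints also stands. The study is non-confirmatory, and protocol 11.8 plans no formal testing of secondary variables.

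**Conclusion.** The point holds as a defect in the secondary stool models. They require a covariate that some subjects may not have, no rule says which run-in days supply it, and nothing says what happens to a subject without one. The loss runs from 65% of subjects (3 per week, Day -1 only, Poisson) to none (evenly spaced stools at 1 per day or more, or at any rate with three days). With Poisson counts some loss remains even when all three days count: 28%, 5% or 0.2%. Against this, the covariate improves the SE of the treatment difference by about 1.4% or less on average, so losing even one subject usually costs more than it gains.

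The size rests on assumptions outside the documents: the stool pattern, the intraclass and baseline correlations, and the drop-out pattern. The mechanism and the missing definition rest on the text alone. The effect is on precision and on which subjects are represented. The primary conclusion is untouched, since the primary variables are counts.

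**What to change.** Preferred: remove the baseline term from the consistency, pH and weight models in SAP 6.2.3. The SAP's model for the three-day total of BSC 6 or 7 stools already has none. Every subject with a treatment-period value then contributes. A treatment collection without a stool still yields no outcome, which this change does not address.

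Alternative: keep the term, define baseline as the mean over all stools available in the run-in (for pH possibly Days -2 and -1 only), and state how subjects who still have none are retained, for example by fitting the model without the covariate.

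In either case, define baseline for these endpoints, because the change-from-baseline summaries in SAP 6.2.2 need it. Leave the per-stool definition of weight as it is and do not code stool-free days as 0.

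Cost: an SAP amendment before database lock, and a documented departure from protocol 11.5.1, from which the SAP already differs by making subject random. Removing the term gives slightly wider CIs for the per-treatment LS means and a negligible loss of precision for treatment differences when periods are incomplete. No new data are needed.
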